9.7 Study Population

The **safety set** will consist of all subjects who have been randomized and who have received at least 1 dose of investigational product.

The **PK set** will consist of all subjects in the safety set for whom the primary PK data are considered sufficient and interpretable.

The **PD set** will consist of all subjects in the safety set for whom the primary PD data are evaluable.

9.8 Pharmacokinetic and Pharmacodynamic Analyses

9.8.1 Pharmacokinetic Analysis

All PK analyses will be performed using the PK set.

Plasma concentrations of SHP639 will be measured using a fully validated bioanalytical method. If data permit, PK parameters for SHP639 will be calculated based on plasma concentration-time data using a noncompartmental approach (Phoenix[®] WinNonlin[®] version 6.4 or higher, Certara USA, Inc, Princeton, NJ, 08540).

9.8.1.1 Pharmacokinetic Endpoints

If data permit, PK parameters will be estimated as appropriate and may include, but are not limited to, the following:

- Maximum observed concentration (C_{\max})
- Time to reach C_{\max} (t_{\max})
- Area under the observed concentration vs time curve:
 - From time zero (predose) to the time of the last measurable concentration (AUC_{0-t})
 - Over the dosing interval ($AUC_{0-\tau}$) for each multiple-dose regimen including QD, BID, TID, and QID
 - From time zero (predose) extrapolated to infinity ($AUC_{0-\infty}$) for QD dosing
- Apparent terminal phase elimination half-life ($t_{1/2}$)
- Apparent clearance (CL/F)
- Apparent volume of distribution (V_z/F)
- Accumulation ratio based on AUC for each multiple-dose regimen, calculated as $AUC_{0-\tau}$ (Day 27)/ $AUC_{0-\tau}$ (Day 1) ($R_{ac[AUC]}$)
- Accumulation ratio based on C_{\max} for each multiple-dose regimen, calculated as C_{\max} (Day 27)/ C_{\max} (Day 1) ($R_{ac[C_{\max}]}$)

9.8.1.2 Statistical Analysis of Pharmacokinetic Parameters

Summary statistics (number of observations, mean, standard deviation [SD], coefficient of variation, median, maximum [max], minimum [min], and geometric mean) will be determined

for all plasma PK parameters and will be presented by dose, cohort, treatment period (single dose or multiple dose; Cohort A only), and study day. Plasma concentrations at each nominal sampling time will also be summarized using descriptive statistics.

For accumulation ratios, the 95% confidence interval (CI) for the arithmetic mean of the difference (for example, $AUC_{0-\tau}$ [Day 28] - $AUC_{0-\tau}$ [Day 1]) on the logarithmic scale (natural base) will be calculated. The results will be back-transformed to give the ratio of geometric means together with the corresponding 95% CI.

Before statistical comparisons, dose-dependent parameters (C_{max} , AUC_{0-t} , $AUC_{0-\tau}$, and $AUC_{0-\infty}$) will be normalized to a common dose, assuming linearity. Additionally, the linear dose proportionality will be evaluated for C_{max} , $AUC_{0-\tau}$, AUC_{0-t} , and $AUC_{0-\infty}$ using the power function model (eg, $C_{max} = \alpha \cdot Dose^{\beta}$ or equivalently $\log[C_{max}] = \log[\alpha] + \beta \cdot \log[Dose]$, where C_{max} is considered to increase linearly proportional to dose if β is not significantly different from 1.0) (Gough et al., 1995).

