3. STUDY DESIGN

3.1 Study Design and Flow Chart

This is a multicenter, randomized, double-masked, placebo-controlled, single- and multiple-dose escalation study. Three different SHP639 concentrations will be studied: 0.1%, 0.3%, and 0.6%. There will be up to 12 cohorts in total, 1 cohort for each dose level and different dosing regimen. Each cohort will consist of 7 subjects for a total of 84 subjects in the study. Eligible subjects will be randomized in a 5:2 ratio to receive either SHP639 or placebo, respectively. The anticipated doses being studied for each dosing regimen are presented in the dose-escalation scheme in [Table 10](#).

A sufficient number of subjects will be screened and enrolled to ensure that at least 6 of 7 subjects complete each treatment in their assigned cohort. In the event that a sufficient number of subjects do not complete a cohort, replacement subjects may be enrolled. Each replacement subject will follow the same screening procedures and randomization sequence as the subject who is discontinued, regardless of when the subject discontinued.

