6. INVESTIGATIONAL PRODUCT

6.1 Identity of Investigational Product

The test product is SHP639 ophthalmic solution, which will be provided as an ophthalmic solution packaged in 7.5 mL (filled to 5 mL) multiuse eye drop bottles. SHP639 ophthalmic solution is a sterile, colorless topical solution containing 0.1%, 0.3%, or 0.6% SRD006086 (as free-base equivalent). The SHP639 ophthalmic solution is preserved with benzalkonium chloride and will be supplied in a multiuse low-density polyethylene eye drop bottle. Additional information is provided in the current SHP639 IB.

The quantities of SHP639 drug substance per drop of SHP639 ophthalmic solution are shown in [Table 9](#).

Table 9 SHP639 Drug Substance per Drop of SHP639 Ophthalmic Solution

Topical Concentration (% weight/volume)	Quantity of SH639 Drug Substance per Drop (µg)
0.1	35
0.3	104
0.6	208

Quantities of drug substance per drop were calculated using a drop volume of 34.7 µL, which was the mean volume obtained at various temperatures, bottle orientations, and concentrations. Values have been rounded to the nearest microgram.

The reference product is placebo, which will be provided as an ophthalmic solution packaged in 7.5 mL (filled to 5 mL) multiuse eye drop bottles identical to those used for the SHP639 ophthalmic solution. The placebo solution will contain the same excipients as the SHP639 ophthalmic solution but will not contain SHP639.

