6.2.3.2 Dose Escalation

Throughout the study, dose escalation meetings will commence at regular time points to review safety data and authorize progression into the next cohort. The anticipated dose escalation scheme is presented in Table 10.

- Single-dose cohorts: a dose escalation meeting may convene after a minimum of 6 subjects have completed the 24-hour assessments for the SDTP. At the dose escalation meeting, a preselected Dose Escalation Committee will determine whether it is safe to continue to the anticipated cohort at either the next dose level or the next dosing regimen.
- Multiple-dose cohorts: a dose escalation meeting may convene after a minimum of 6 subjects have completed the Day 14 assessments for the MDTP. At the dose escalation meeting, a preselected Dose Escalation Committee will determine whether it is safe to continue to the anticipated cohort at either the next dose level or the next dosing regimen. If the dose escalation meeting was held prior to the completion of the cohort, the remainder of the treatment period will be completed following the dose escalation meeting.

Table 10 Anticipated Dose-escalation Scheme

Dose Authorized by Committee			Enabling Required Dose-escalation Activity					
			Before Switch from Single to Multiple Dose - BID, TID, or QID			Before Increasing Dose Level		
Cohort	Dose	Regimen	Cohort	Dose	Regimen	Cohort	Dose	Regimen
A1	0.1%/Placebo	SD	NA	–	–	NA	–	–
A1	0.1%/Placebo	QD	A1	0.1%/Placebo	SD	NA	–	–
A2	0.3%/Placebo	SD	NA	–	–	A1	0.1%/Placebo	SD
A2	0.3%/Placebo	QD	A2	0.3%/Placebo	SD	A1	0.1%/Placebo	QD
A3	0.6%/Placebo	SD	NA	–	–	A2	0.3%/Placebo	SD
A3	0.6%/Placebo	QD	A3	0.6%/Placebo	SD	A2	0.3%/Placebo	QD
B1	0.1%/Placebo	BID	A1	0.1%/Placebo	QD	NA	/–	–
B2	0.3%/Placebo	BID	A2	0.3%/Placebo	QD	B1	0.1%/Placebo	BID
B3	0.6%/Placebo	BID	A3	0.6%/Placebo	QD	B2	0.3%/Placebo	BID
C1	0.1%/Placebo	TID	B1	0.1%/Placebo	BID	NA	/–	–
C2	0.3%/Placebo	TID	B2	0.3%/Placebo	BID	C1	0.1%/Placebo	TID
C3	0.6%/Placebo	TID	B3	0.6%/Placebo	BID	C2	0.3%/Placebo	TID
D1 ^a	0.1%/Placebo	QID	C1	0.1%/Placebo	TID	NA	–/	–
D2	0.3%/Placebo	QID	C2	0.3%/Placebo	TID	D1	0.1%/Placebo	QID
D3	0.6%/Placebo	QID	C3	0.6%/Placebo	TID	D2	0.3%/Placebo	QID

BID=twice daily; NA= not applicable; QD=once daily; QID=4 times daily; SD=single dose; TID=3 times daily.

^a Cohort D1 is not to be enrolled as it was decided that the resulting data would not contribute to the understanding of the safety of SHP639.

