9.6 Sample Size Calculation and Power Considerations

A sufficient number of subjects will be screened to ensure the enrollment and completion of 84 subjects.

The number of subjects in this study is not based on statistical power considerations because the statistical analyses are primarily descriptive in nature. However, if at least 7 subjects complete each cohort, then there will be at least 65% to 85% probability of observing at least 1 occurrence of any AE with a true incidence rate for a given dose group of at least 15-25%, respectively.

It is estimated that dose escalation will occur for up to 3 dose levels (4 cohorts within each dose level). Each cohort will include 5 subjects randomized to active drug and 2 subjects randomized to placebo for an estimated total of at least 84 subjects.

For each cohort, the number of subjects will be increased as needed based on safety and IOP response. Any cohort can be repeated to confirm findings with regard to safety or IOP response.

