12.3 Statistical Analysis of Pharmacokinetic Data

For each of SD, QD, BID, TID and QID dosing regimens, if sufficient data are available across dose groups, dose proportionality of plasma SHP639 PK variables $AUC_{0-\infty}$, AUC_{0-t} , $AUC_{0-\tau}$, and C_{max} over the dose ranges tested will be investigated. For Days 1 and 27 for MDTP of all cohorts, the following power model will be used to assess dose proportionality. The model is defined as:

$$\ln(\text{PK parameter}) = a + b * \ln(\text{dose}),$$

where 'a' is the intercept and 'b' is the slope of the line. The 95% confidence interval (CI) of the estimate of parameter 'b' will be presented. A 95% CI of the slope that includes 1.0 will be interpreted as the absence of significant evidence of non-proportionality.

For statistical analysis of accumulation of SHP639, a linear mixed-effect model with day, dose, and day and dose interaction term as fixed effects and subject as random effect will be fitted to the natural log-transformed C_{max} and $AUC_{0-\tau}$ to construct 95% CIs for Day 27 compared with Day 1 for each of QD, BID, TID, and QID dosing regimens separately. Statistical analysis to assess dose proportionality and accumulation of SHP639 will be conducted using SAS for Windows® (Version 9.3 or higher).

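### Protocol 9.8.1.2 takes a non-significant slope test as proof of dose proportionality, while SAP 12.3 draws a weaker conclusion from the same result; the protocol's verdict should be removed

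*Protocol*

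**What the plan says.** Protocol 9.8.1.2, repeated in the synopsis under the PK statistical methodology, regresses log exposure on log dose and says that Cmax, as the example parameter, "is considered to increase linearly proportional to dose if β is not significantly different from 1.0". It gives no significance level, margin or power for this test, and does not say whether the model is fitted per regimen or across regimens.

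SAP 12.3 supplies the detail. The scope is "For each of SD, QD, BID, TID and QID dosing regimens, if sufficient data are available across dose groups". On output: "The 95% confidence interval (CI) of the estimate of parameter 'b' will be presented". On interpretation: "A 95% CI of the slope that includes 1.0 will be interpreted as the absence of significant evidence of non-proportionality".

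On sample size, Protocol 9.6 states: "Each cohort will include 5 subjects randomized to active drug and 2 subjects randomized to placebo". The concentrations are 0.1%, 0.3% and 0.6% (Protocol 3.1). For QID, footnote a to Table 10 in Protocol 6.2.3.2 says: "Cohort D1 is not to be enrolled as it was decided that the resulting data would not contribute to the understanding of the safety". QID therefore has 0.3% and 0.6% only.

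**The concern.** A non-significant test of slope = 1 shows only that the data did not rule out 1. The protocol turns that into a positive finding. Under such a rule, noisier or sparser data make a verdict of proportionality more likely, which is the wrong way round.

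The SAP words the same outcome more carefully, but nothing in SAP 12.3 says that it replaces the protocol's sentence, and SAP Section 1 presents the SAP as an elaboration of Protocol Amendment 3. A report author could therefore write either that exposure is proportional to dose (protocol) or that there is no significant evidence that it is not (SAP), from one and the same CI. At stake is how plasma exposure across concentrations is described. The risk is greatest for QID, where two doses only two-fold apart leave the slope poorly estimated.

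**Working it through.** The documents state no power, precision or variability for dose proportionality, so there is no plan figure to reproduce.

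**Inputs from the documents**
- 5 active subjects per dose (Protocol 9.6).
- One model per regimen and a 95% CI, hence a two-sided 5% test (SAP 12.3).
- Three doses, 0.1/0.3/0.6%; QID 0.3/0.6% only.

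**Assumptions (not in the documents)**
- Between-subject CV of 20–100%.
- True slope of 0.75 as the departure of interest. Over a 6-fold dose range, exposure then rises 6^0.75 = 3.83-fold, and dose-normalised exposure is 1 − 6^(−0.25) = 36% lower at the top dose. Over QID's 2-fold range the same slope means 1 − 2^(−0.25) = 16% lower.

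**Formulas**
- σ = √ln(1 + CV²) on the log scale.
- SE(slope) = σ/√Sxx, where Sxx is the sum of squared deviations of ln(dose).
- CI half-width = t(0.975, df) × SE, with df = N − 2.
- P(called proportional) = P(|T| < t(0.975, df)), with T noncentral t and noncentrality (0.75 − 1)/SE.

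**Design constants**
- Three doses × 5: deviations of ln(dose) from their mean are −0.9635, 0.1351 and 0.8283. Sxx = 5 × (0.9283 + 0.0183 + 0.6861) = 8.16; df 13; t = 2.160.
- QID: Sxx = 5 × (ln 2)²/2 = 1.20; df 8; t = 2.306.

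**Worked example, CV 50%**
- σ = √ln 1.25 = 0.472.
- Three doses: SE = 0.472/√8.16 = 0.165; half-width 0.36; noncentrality −1.51; P = 71%.
- QID: SE = 0.472/√1.20 = 0.431; half-width 0.99; noncentrality −0.58; P = 92%.

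| CV | Three-dose half-width | Three-dose: slope 0.75 called proportional | QID half-width | QID: slope 0.75 called proportional |
|---|---|---|---|---|
| 20% | 0.15 | 8.5% | 0.42 | 77% |
| 25% | 0.19 | 23.5% | 0.52 | 83% |
| 30% | 0.22 | 38.5% | 0.62 | 87% |
| 50% | 0.36 | 71% | 0.99 | 92% |
| 70% | 0.48 | 82% | 1.33 | 93% |
| 100% | 0.63 | 87.5% | 1.75 | 94% |

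With the per-drop doses of Protocol Table 9 (35, 104 and 208 µg; Sxx 8.07), the three-dose ends for CV 30–100% are 39.0% and 87.6%, hence about 39–88%.

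**Sensitivities**
- Repeat of B3: SAP 13 says it took place but not how many subjects it added. If it added 5 active subjects at 0.6% BID (Sxx 10.74, df 18), the BID figures are 25/62/77/85% at CV 30/50/70/100%.
- Larger departure, three doses, slope 0.5: 0.6% at CV 30%, 20% at CV 50%, 64% at CV 100%.
- QID with no rise in exposure at all (slope 0): called proportional 10/47/67/79% of the time at CV 30/50/70/100%.
- One model across all 11 remaining cohorts on dose per drop, which the protocol's wording does not exclude: 1–66% at slope 0.75 over CV 30–100%.

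**The case against.** The strongest answer is that the SAP already handles this. Protocol 9.4 leaves PK methods and definitions to the SAP. SAP 12.3 presents the CI and reads a CI containing 1.0 correctly, without concluding proportionality. On that view only a wording mismatch is left. This largely stands and sets the size of the point. It does not dispose of it, because the protocol sentence is still in force in two places.

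A second answer is that little depends on the result. PK enters only the exploratory PK-PD objective (Protocol 2.2.3). Escalation under Protocol 6.2.3.2 rests on safety review. SAP 12.6 plots PK against PD parameters directly. The model is conditional on sufficient data, and Protocol 1.2.1 reports very low to undetectable systemic exposure in animals after topical dosing, so it may never be fitted. All of this stands and makes the impact modest.

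A third is that the percentages rest on a CV and a slope that the documents do not give. That is so, and the three-dose figure drops to 9–24% at CV 20–25%. The flaw in the inference does not depend on the CV, and the QID figure is 77% even at CV 20%, although slope 0.75 is a smaller departure over QID's 2-fold range.

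Finally, Protocol 9.6 calls the analyses primarily descriptive. A descriptive analysis would report the slope and CI with no verdict attached, which is what the fix asks for.

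**Conclusion.** The protocol's rule is wrong as written, and it conflicts with the SAP's reading of the same CI. On the assumptions above (CV 30–100%, 5 active per dose, per-regimen fit), it would call a true slope of 0.75 proportional about 39–88% of the time in three-dose regimens and 87–94% in QID, where the expected CI half-width is about 0.6–1.75. If the B3 repeat added 5 active subjects, BID would be 25–85%. The correction is worth making because it is nearly free; the consequences are modest.

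A reader might infer more than the documents support:
- *That the SAP also declares proportionality.* It shares the trigger but not the conclusion.
- *That the rule misses most non-proportional truths.* At slope 0.5 with three doses it misses 0.6% at CV 30% and 20% at CV 50%.
- *That QID usually cannot exclude a flat dose response.* For a truly proportional drug, the 95% CI includes 0 only 10% of the time at CV 30%; this rises to 47% at CV 50% and 79% at CV 100%.
- *That a false verdict would validate the protocol's dose normalisation or affect escalation.* The protocol lists normalisation as a separate, prior step, the SAP's output list contains no dose-normalised output, and no stated escalation criterion uses the slope.

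**What to change.** 1. In Protocol 9.8.1.2 and the synopsis, delete the clause "is considered to increase linearly proportional to dose if β is not significantly different from 1.0".
2. In the protocol and SAP 12.3, state that the slope and its CI will be reported for each regimen for which the model is fitted, that a CI containing 1 does not establish proportionality, and that a wide CI (notably from two-dose QID) will be reported as inconclusive.

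The model and the output stay the same, so the cost is a protocol clarification and a sentence in the SAP. The downside is that the study can no longer claim proportionality from a non-significant test.

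A formal acceptance range is optional. One common form requires the 90% CI to lie within 1 ± ln(1.25)/ln(r), with r the ratio of highest to lowest dose: 0.875–1.125 for r = 6 and 0.68–1.32 for r = 2. At this sample size it would rarely be met. With a true slope of exactly 1 and three doses, simulation gives about 13% at CV 20%, 0.6% at CV 30% and close to 0 at CV 50%; for QID it gives 1.2% at CV 30% and 0.03% at CV 50%. Reporting the estimate and CI without a verdict is enough.

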9.8.2 Pharmacodynamic Analysis

All the PD analyses will be performed using the PD set. Intraocular pressure (mmHg) will be measured using Goldmann applanation tonometry.

9.8.2.1 Pharmacodynamic Endpoints

Pharmacodynamic parameters will be estimated as appropriate and may include, but are not limited to, the following:

- Change from baseline in IOP
- Time to the maximum change from baseline in IOP
- Proportion of subjects maintaining IOP reduction after specified days of treatment

Specific endpoints in order to understand the effect of SHP639 on IOP will be defined in the SAP.

9.8.2.2 Statistical Analysis of Pharmacodynamic Parameters

Descriptive summary statistics for IOP (number of subjects, mean, SD, median, min, and max) will be calculated by dose, cohort, treatment period (single dose or multiple dose; Cohort A only), study day, and time point (for days with multiple assessments per day). Additionally, 95% CIs for each estimate and summary statistics of change from baseline and percentage change from baseline, along with 95% CIs, will be calculated. Pharmacodynamic parameters will be calculated and summarized by dose, cohort, treatment period (single dose or multiple dose; Cohort A only), and study day as applicable.

All IOP data will be listed by dose, cohort, subject, treatment period (single dose or multiple dose; Cohort A only), and study day.

9.8.3 Pharmacokinetic and Pharmacodynamic Analysis

The relationship between dose of SHP639 ophthalmic solution, plasma PK parameters, and changes in IOP may be explored using graphical and/or regression methods if the data permit.

Further details of PK, PD, and PK-PD analyses will be presented in the SAP.

9.9 Safety Analyses

9.9.1 Safety Endpoints

Safety and tolerability will be assessed by monitoring AEs, vital sign measurements, clinical laboratory assays, ECGs, ADA, drop comfort assessment, and ophthalmologic examinations.

9.9.2 Statistical Analysis of Safety Data

The placebo subjects will be pooled together as a pooled placebo group.

All vital sign, clinical laboratory, ECG, ADA, drop comfort assessment, and ophthalmologic examination data (per schedule of events) will be listed by dose, cohort, subject, treatment period (single dose or multiple dose; Cohort A only), visit, day, and time point (for days with multiple assessments per day). If the ranges are available then abnormalities will be flagged. Summary statistics with number of subjects, mean, SD, median, minimum, and maximum will be provided by dose, cohort, treatment period (single dose or multiple dose; Cohort A only), visit, day, and time point (for days with multiple assessments per day).

Adverse events will be coded using the Medical Dictionary for Regulatory Activities. The number of events, incidence, and percentage of treatment-emergent AEs will be calculated overall and by system organ class and preferred term by dose and cohort. Treatment-emergent AEs will be further summarized by severity and relationship to investigational product. Adverse events related to investigational product, AEs leading to withdrawal, SAEs, and deaths will be similarly summarized/listed. All information obtained on AEs will be displayed by dose, cohort, subject, treatment period (single dose or multiple dose; Cohort A only), visit, and day. A subject with multiple AEs within a body system will be counted only once.

9.10 Other Analyses

No other analyses are planned in this study.

10. SPONSOR'S AND INVESTIGATOR'S RESPONSIBILITIES

This study is conducted in accordance with current applicable regulations including ICH E6, EU Directive 2001/20/EC, and all updates, as well as local ethical and legal requirements.

Compliance with these regulations and guidelines also constitutes compliance with the ethical principles described in the Declaration of Helsinki

The name and address of each third-party vendor (eg, CRO) used in this study will be maintained in the investigator's and sponsor's files, as appropriate.

10.1 Sponsor's Responsibilities

10.1.1 Good Clinical Practice Compliance

The study sponsor and any third party to whom aspects of the study management or monitoring have been delegated will undertake their assigned roles for this study in compliance with all applicable industry regulations and ICH GCP Guideline E6 (1996), EU Directive 2001/20/EC, as well as all applicable national and local laws and regulations.

Visits to sites are conducted by representatives of the study sponsor and/or the company organizing/managing the research on behalf of the sponsor to inspect study data, subjects' medical records, and eCRFs in accordance with current GCP and the respective local and international/national government regulations and guidelines. Records and data may additionally be reviewed by auditors or by regulatory authorities.

The sponsor ensures that local regulatory authority requirements are met before the start of the study. The sponsor (or a nominated designee) is responsible for the preparation, submission, and confirmation of receipt of any regulatory authority approvals required before release of investigational product for shipment to the site.

